PLANNED START OF STUDY		Estimated study duration	
PRINCIPAL INVESTIGATOR	[name], FNP-C, NRCME, CCM		
STUDY SITE	Atlantia Clinical Trials, [name]		
RESEARCH AREA/APPLICATION FIELD	Constipation		
PRIMARY OBJECTIVE	To evaluate the effect of eight weeks daily consumption of B. longum compared to Placebo on Spontaneous Bowel Movement (SBM) frequency, in a population who experience constipation.		
SECONDARY OBJECTIVES	To evaluate the effect of eight weeks daily consumption of B. longum compared to Placebo, in a population who experience constipation on: 
 - SBM frequency measured by the daily bowel diary from baseline to week 6. - Stool consistency as assessed by the Bristol Stool Scale (BSS). - Constipation related symptoms as assessed by Patient Assessment of Constipation Symptoms (PAC-SYM) Total Score. - Impact of constipation on Quality of life as assessed by Patient Assessment of Constipation Quality of Life Questionnaire (PAC-QoL) Total Score. 		
SAFETY AND TOLERABILITY OBJECTIVES	To evaluate in otherwise healthy adults with constipation, the safety and tolerability of consuming two capsules of B. longum consumed daily compared to Placebo as assessed by: 
 - Occurrence of any Adverse Events (AEs/SAEs) - Vital signs (Blood Pressure, Heart Rate, and Temperature) - Safety blood parameters 		
STUDY DESIGN	Randomized, double-blinded, placebo-controlled, parallel study in healthy adults.		
STUDY POPULATION	Otherwise, generally healthy adults aged 18 to 65 who regularly experience constipation.		
SAMPLE SIZE	Screen $n = 160$ Randomize $n = 80$ (Two arms with 40 subjects per group) Evaluable $n = 72$ Expected dropout rate is 10% - dropouts will not be replaced.		

NUMBER OF SITES	Single centre; Atlantia Clinical Trials, [name]		
STUDY PRODUCT	I. B. longum II. Placebo		
NUMBER OF ARMS	2		
DOSAGE AND REGIMEN	Two capsules of the Study Product per day, before breakfast, with a glass of water for the duration of the study (56 days).		
PARTICIPANT CRITERIA	SELECTION	
Inclusion criteria:
 
To be eligible for inclusion, the Participant must fulfil all the following criteria:
 
 1. Is willing to participate in the study and comply with its procedures. 2. Be able to give written informed consent. 3. Adults aged ≥ 18 years and ≤ 65 years. 4. Experience less than 3 bowel movements per week within the past three months. 5. $\geq 25\%$ of bowel movements with stool firmness, less than Type-3 based on Bristol Stool Scale (BSS), within the past three months. 6. Record less than 6 bowel movements in eDiary App during the two-week run-in period. 7. Is willing to maintain the current diet and level of physical activity throughout the study period. 
Exclusion criteria:
 
The presence of any of the following criteria will exclude the Participant from participating in the study:
 
 1. Participants who are pregnant or wish to become pregnant during the study, or who are currently breastfeeding. 2. Participants currently of childbearing potential, but not using continuous effective method of contraception, as outlined below: 
 a. Complete abstinence from intercourse two weeks prior to administration of the Study Product, throughout the clinical study, until the completion of follow-up procedures or for two weeks following discontinuation of the Study Product in cases where Participant discontinues the study prematurely. (Participants utilizing this method must agree to use an alternate method of contraception if they should become sexually active and will be queried on whether they have been abstinent in the preceding two weeks when they present to the clinic for the final Visit). b. Has a male sexual partner who is surgically sterilized prior to the Screening Visit and is the only male sexual partner for that Participant. c. Sexual partner(s) is/are exclusively female. d. Use of acceptable method of contraception, such as a spermicide, mechanical barrier (e.g., male condom, female diaphragm), tubal ligation, or contraceptive pill. The 	

[figure not shown]
	
Participant must be using this method for at least one week prior to and one week following the end of the study.
 
 e. Use of any intrauterine device (IUD) or contraceptive implant. The Participant must have the device inserted at least two weeks prior to the first Screening Visit, throughout the study, and two weeks following the end of the study. 3. Participants reporting current, or historical alcohol or drug abuse in past year. 4. Participants who have quit smoking in the 6-months prior to screening. 5. Participants with a known allergy to the Study Product's active or inactive ingredients. 6. Participants with a chronic disease who require long-term medication throughout the whole study period. 7. Participants with a significant acute, chronic or un-controlled coexisting illness or is taking medication/supplements that would put the Participant at risk or confound the interpretation of the study results, as judged by the investigator. 8. Participants who regularly take medications, that are thought to affect defecation, including regular laxative use. (Occasional laxative use (PRN) < 3 times per month is acceptable). 9. Participants who regularly consume supplements that are thought to affect defecation, including but not limited to fiber, iron, and magnesium. 10. Participants who are consuming oral antibiotics at screening, during run-in and for the duration of the study. 11. Participants who have consumed probiotic supplements and prebiotic supplements eight weeks prior to Visit 2. 12. Participants who have consumed fermented foods, that aid in bowel movement improvement such as yogurt, kefir, sauerkraut, kimchi, soy-based fermented food, miso, natto and fermented cheese, etc. within the four weeks prior to the Visit 2. 13. Participants who are diagnosed with or undergoing treatment for any gastrointestinal conditions such as coeliac disease, diarrhea, Crohn's disease, ulcerative colitis, irritable bowel syndrome, diverticulosis, stomach or duodenal ulcers, gastroesophageal reflux disease (GERD) or have undergone significant gastrointestinal surgery (appendectomy allowed). 14. Participants diagnosed with clinical depression, Parkinson's disease, anxiety or an anxiety related disorder, who are undergoing treatment with medication. 15. Participants with clinically significant abnormal laboratory results at screening. 16. Individuals who are cognitively impaired and/or who are unable to give informed consent. 17. Participants may not be participating in other clinical studies. If the participant has previously taken part in an experimental study, the
--	-----------------------------------------------------------------------------------------------------------------------------------------------------------------------------------------------------------------------------------------------------------------------------------------------------------------------------------------------------------------------------------------------------------------------------------------------------------------------------------------------------------------------------------------------------------------------------------------------------------------------------------------------------------------------------------------------------------------------------------------------------------------------------------------------------------------------------------------------------------------------------------------------------------------------------------------------------------------------------------------------------------------------------------------------------------------------------------------------------------------------------------------------------------------------------------------------------------------------------------------------------------------------------------------------------------------------------------------------------------------------------------------------------------------------------------------------------------------------------------------------------------------------------------------------------------------------------------------------------------------------------------------------------------------------------------------------------------------------------------------------------------------------------------------------------------------------------------------------------------------------------------------------------------------------------------------------------------------------------------------------------------------------------------------------------------------------------------------------------------------------------------------------------------------------------------------------------------------------------------------------------------------------------------------------------------------------------------------------------------------------------------------------------------------------------------------------------------------------------------------------------------------------------------------------------------------------------------------------------------------------------------------------------------------------------------------------------------------------------------------------------------------------------------------------------------------------------------------------------------------------------------------------------------

	
Investigator must ensure sufficient time has elapsed before entry to this study to ensure the integrity of the results.
 
18. Any Participant who is an employee of the investigational site or an Atlantia Clinical Trials employee or their close family member or a member of their household.
 
19. Individuals who, in the opinion of the investigator, are considered to be poor attendees or unlikely for any reason to be able to comply with the study.

STATISTICAL CONSIDERATIONS	
All statistical elements of the study will be informed by the principles of the International Conference on Harmonization -Good Clinical Practice (ICH-GCP) documents and executed by the study statistician under the standard operating procedures for Atlantia Clinical Trials Ltd. Details about these elements will be available in a Statistical Analysis Plan (SAP) which will be written prior to first Participant randomized and finalized prior to database lock. Any deviations from the SAP and/or additional analysis after database lock should be fully described and justified in the clinical study report. The SAP will be developed by the study statistician, in close collaboration with the study PI and study Sponsor. All analyses will be conducted using IBM SPSS Statistics Software with figures generated using GGPLOT script in e R Project for Statistical Computing, as appropriate. Reporting of the statistical results will be informed by the principles of ICH-GCP and CONSORT.

ETHICAL, LEGAL, AND REGULATORY REQUIREMENTS	
An application will be submitted to the Institutional Review Board (IRB) for approval of the study, prior to the study starting.
 
This study will be conducted according to the principles of ICH-GCP and the Declaration of Helsinki.
 
The study will be registered by Morinaga Milk Industry at clinicaltrials.gov.

Study Overview

Abbreviations

AE	Adverse Event
AR	Adverse Reaction
BDR	Blinded Data Review
BMI	Body Mass Index
BSS	Bristol Stool Scale
CFU	Colony Forming Units
CONSORT	Consolidated Standards of Reporting Trials
CRF	Case Report Form
eCRF	Electronic Case Report Form
EDC	Electronic Data Capture
EP	Enrolled Population
GERD	Gastroesophageal Reflux Disease
GI	Gastrointestinal
GRAS	Generally Recognized As Safe
ICH-GCP	International Council for Harmonization- Good Clinical Practice
IDMC	Independent Data Monitoring Committee
IEC/IRB	Independent Ethics Committee/Institutional Review Board
ISF	Investigator Site File
ITT	Intention-to-Treat

1.1 Background information

Probiotics have been reported to have a beneficial effect on the intestines, and Bifidobacteria, in particular, have shown functionality in relieving constipation⁽¹⁾. For this study, bowel movements are defined as any bowel movement, irrespective of its characteristics. In contrast, Spontaneous Bowel Movements (SBM) are defined as no manual maneuver and no laxatives, enemas, or suppositories in the preceding 24 hours. To obtain a holistic understanding of the effect of *B. longum* on gastrointestinal function, it is essential to select an appropriate type of bowel movement as an evaluating indicator. SBMs represent a natural and unstimulated event that reflects the body's ability to regulate bowel movements without external factors. Including SBMs in the study allows for a more comprehensive evaluation of bowel function.

1.2 Study Product

B. longum, which is isolated from infants, has been proven to be safe and has been widely used in fermented foods and supplements for a long time.

In this study, the active Study Product, *B. longum* capsule, contains lyophilized powder of live *B. longum* at 5×10^9 CFU/capsule blended with corn starch, and placebo capsule contains corn starch only.

High survivability of *B. longum* in host feces has been identified after oral intake. As a bifidobacteria, *B. longum* produces not only lactic acid but also a significant amount of acetic acid in the colon, which can reduce the luminal pH and improve the bowel movement. It is considered that *B. longum* can promote defecation and improve constipation.

1.3 Rationale for conducting the clinical study

Due to limitations in recruiting clinical subjects, previous clinical trials investigating the effects of *B. longum* on constipation improvement only focused on East Asian individuals as participants. Consequently, there is currently a lack of clinical evidence regarding the efficacy of *B. longum* in regulation of bowel movement frequency and determining the appropriate dosage for European and North American populations, which have significantly different ethnicities, diets, and lifestyle habits.

2 Objectives

2.1 Primary objective

To evaluate the effect of eight weeks daily consumption of *B. longum* compared to Placebo on Spontaneous Bowel Movement (SBM) frequency, in a population who experience constipation.

2.1.1 Primary endpoint

Change in mean weekly frequency of SBM, as measured by the daily bowel diary from baseline to the end of intervention. Frequency will be defined as the mean weekly number of SBM during the 2-week run-in period prior to Visit 2, for baseline, and during the final 2-week period of the intervention prior to Visit 3, for end of intervention.

2.2 Secondary objectives

To evaluate the effect of eight weeks daily consumption of *B. longum* compared to Placebo, in a population who experience constipation on:

- SBM frequency measured by the daily bowel diary from baseline to week 6.
- Stool consistency as assessed by the Bristol Stool Scale (BSS).
- Constipation related symptoms as assessed by Patient Assessment of Constipation Symptoms (PAC-SYM) Total Score.
- Impact of constipation on Quality of life as assessed by Patient Assessment of Constipation Quality of Life Questionnaire (PAC-QoL) Total Score.

2.2.1 Secondary endpoints

- Change in mean weekly frequency of SBM, as measured by the daily bowel diary from baseline to Week 6. Frequency will be defined as the mean weekly number of SBM from baseline to Week 1-2, baseline to Week 3 -4, baseline to Week 5-6.
- Change in mean daily stool consistency as measured from the Bristol Stool Scale (BSS) in the daily bowel diary from baseline to the end of intervention. Stool Consistency will be defined as the mean daily stool consistency during the 2-week run-in period prior to Visit 2, for baseline, and during the final 2-week period of the intervention, for end of intervention.
- Change in self-reported constipation related symptoms as assessed by the Total Score of the Patient Assessment of Constipation Symptoms (PAC-SYM) Questionnaire from baseline to:
 - Week 4
 - Week 8
- Change in self-reported impact of constipation on Quality of Life as assessed by the Total Score of the Patient Assessment of Constipation Quality of Life (PAC-QoL) Questionnaire from baseline to:
 - Week 4
 - Week 8

2.3 Exploratory objective(s)

To evaluate the effect of eight weeks daily consumption of *B. longum* compared to Placebo, in a population who experience constipation on:

- PAC-SYM sub-scores (Abdominal, Rectal, and Stool related symptoms)
- PAC-QoL sub-scores (Physical Discomfort, Psychosocial Discomfort, Treatment Satisfaction, and Worries/ Concerns)
- Microbiome and fecal metabolite analysis (stool sampling only, analysis by Morinaga Milk Industry)

2.3.1 Exploratory endpoints

- Change in PAC-SYM sub-scores (Abdominal, Rectal, and Stool related symptoms) from baseline to:
 - Week 4
 - Week 8
- Change in PAC-QoL sub-scores (Physical Discomfort, Psychosocial Discomfort, Treatment Satisfaction, and Worries/ Concerns) from baseline to:
 - Week 4
 - Week 8

2.4 Safety objectives and tolerability objective(s) and endpoint variables

2.4.1 Safety and tolerability objective(s)

To evaluate in otherwise healthy adults with constipation, the safety and tolerability of *B. longum* consumed twice daily compared to Placebo as assessed by:

- Occurrence of any Adverse Events (AEs/SAEs)
- Vital signs (Blood Pressure, Heart Rate, and Temperature)
- Safety blood parameters

2.4.2 Safety and tolerability endpoint variable(s)

- Incidence of AEs per group by product causality.
- Incidence of mild, moderate, and severe AEs per treatment group by product causality.
- Incidence of AEs by MedDRA System Organ Classification (SOC) and preferred term (PT) by product allocation.
- Incidence of Safety Blood Parameter AEs by product allocation.

- Incidence of Vital Parameter (blood pressure, heart rate, and body temperature) AEs by product allocation.
- Incidence of SAEs per group by product causality.

3 Study Design

Randomized, double-blinded, placebo-controlled, parallel study in healthy adults.

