5.5 Supplementation regimen

5.5.1 Dosage regimen and dose adjustment

- Participants will be provided an eight-week supply of Study Product (5 bags) at Visit 2 in a transparent UniPak, wherein 4 bags will be used for consumption during the eight-week intervention period and 1 bag will be provided as an additional supply in case of delay in study visit or loss of Study Product.
- Participants will be instructed to consume two capsules of the Study Product per day, before breakfast, with a glass of water for the duration of the study (56 days).
- If the dose is missed, the Participant should consume the same dosage after dinner on the same day.
- Missed doses should not be moved to the following day.
- Participants will be instructed to return any unused Study Product at Visit 3.
- Participants will consume their first dose of Study Product on the day following their Visit 2 (Day 1) and will consume their final dose of Study Product on the morning of their Visit 3 (Day 56).

In the event of significant worsening, severe or intolerable new GI symptoms, or other AEs after product consumption/use or overdose, the dose may be interrupted or titrated after consultation with the sponsor representative and PI/Sub-Investigator. The dose may be temporarily interrupted for the shortest time possible without increasing the risk to the Participants continued safety on the study. If the Participant requires dose interruption for more than three days with no improvement in GI symptoms and/or other AEs, then consultation with the Sponsor representative and PI/Sub-Investigator must occur, and the Participant may be discontinued from SP.

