5.9 Rescue Medication

In case of no bowel movement for more than four days: bisacodyl suppositories or tablets (5- 10 mg) or other rescue medication in line with local guidelines at the dose specified in the local guidelines (no more than three consecutive days over a period of 1 week) will be allowed as rescue medication. Maximum dosage: 15 mg/ day.

Its use needs to be documented at relevant study visits (including concomitant medication, diet, supplements, and any related adverse event). The date and time of rescue medication administration as well as the name and dosage regimen of the rescue medication must be recorded.

The study site will not supply any rescue medication.

6 Study Procedures

Table 2. Schedule of Assessments

Assessment periods						
Visit Number	Visit 1	Run-in	Visit 2	Visit 3	Early Termination Visit	
Visit Window	Day -21 to -15	Day -14 to -1	Day 0	Day 56 + 3 Days		
Study Phase	Screening	Run-in	Intervention			
Screening						
Informed consent	x					
Eligibility Screen	x		x			
Demographic/ Lifestyle data	x					
Medical history	x		x		x	
Anthropometric measurements (Height, weight, BMI)	x					
Prior and concomitant medications	x		x	x	x	
Safety and Tolerability						
Vitals (Blood pressure, heart rate, temperature)	x		x	x	x	
Safety blood parameters	x					

Assessment periods						
Visit Number	Visit 1	Run-in	Visit 2	Visit 3	Early Termination Visit	
Visit Window	Day -21 to -15	Day -14 to -1	Day 0	Day 56 + 3 Days		
Study Phase	Screening	Run-in	Intervention			
(Chemistry profile and Hematology profile)						
AE/SAE			<----->		x	
Assessments/Procedures						
Stool sample collection						
Dispense stool collection kit	x		x			
Return Stool Sample for microbiome analysis			x	x	x	
Urine collection						
Urine pregnancy test	x		x	x	x	
Questionnaires						
Download eDiary App	x					
Bowel Movement & Bristol Stool Scale		x	<----->			
PAC-SYM (Week 0, 4 & 8)			<----->			
PAQ-QoL (Week 0, 4 & 8)			<----->			
Delete eDiary App				x	x	
Dietary analysis						
Dispense 3-Day food Diary	x		x			
Return 3-Day food Diary			x	x	x	
Supplementation						
Randomization			x			
Administer SP			x			
Return SP				x	x	
Assess SP Compliance				x	x	
Participant Compensation						
Dispense Participant Compensation				x	x	

All visits will have the option of being completed remotely via telephone where feasible based on the assessments required for the visit.

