8.1 Blood sample collection

A total of approximately 7.5mL/0.25 fl.oz of blood should be collected from all Participants.

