8.4 Analysis of Samples

All samples will be analyzed using validated assays and methods.

9 Early Participant Withdrawal

Participants have the right to withdraw from the study at any time for any reason, without giving a reason and without penalty or loss of benefits they are entitled to. The PI/Sub-Investigator also has the right to discontinue Participants from SP consumption and/or withdrawal from the study if this is in the best interest of the Participant or if Participant is persistently not compliant with study procedures and SP consumption.

Any of the following conditions may lead to premature withdrawal from SP/study:

- Request by Participant to discontinue for any reason during the study.
- erroneously included / randomized Participant.
- adverse event(s) or concurrent illness that, in the opinion of the PI/Sub-Investigator, warrants the Participant's withdrawal from intervention.
- intake of concomitant medication/dietary supplements prohibited by the protocol.
- Participants who do not follow the requirements of the Protocol, especially those concerning safety and/or if the Participant after their enrolment is uncooperative or not willing to comply with the protocol (non-compliant).

- failure to return for follow-up visits despite numerous attempts to reschedule (lost to follow-up).
- request by regulatory agencies for termination of supplementation of an individual Participant or all Participants under this protocol.
- pregnancy, if a protocol exclusion criterion.

The circumstances of any discontinuation will be in consultation with the Sponsor and must be documented in detail in the corresponding study termination form in the case report form. Whenever a Participant will be withdrawn from the study for whatever reason, adequate efforts will be made to perform a final assessment to include standard medical and laboratory tests which would have been done on normal completion of the study. The data of the withdrawn Participants will be documented in the clinical study report.

Note: Participants who withdraw prematurely from the study will not be replaced.

10 Data processing

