11.2.4 Clinical laboratory and other safety evaluations

A change in the value of a clinical laboratory, vital sign, or other study assessment can represent an AE if the change is a clinically significant worsening from baseline. This includes abnormal assessments where there is a shift of a parameter from a normal value to an abnormal value, or a significant worsening of an already abnormal value. Clinical significance is defined as an abnormal study assessment that leads to a diagnosis (in which case the diagnosis is recorded rather than the abnormal assessment) or results in Participant intervention such as further monitoring (excluding confirmatory repeat testing) or medical treatment. If, at the end of the treatment phase, there are abnormal clinical laboratory, vital sign values or other study assessments which were not present pre-treatment, the value observed closest to the start of study treatment should be used as baseline. The PI or Sub-Investigator should decide, based on the above criteria and the clinical condition of a Participant, whether a worsening of an abnormal study assessment is clinically significant and therefore represents an AE.

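### Laboratory adverse events are a between-arm safety endpoint, but the only scheduled safety blood draw is at screening, before anyone takes product

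*Protocol*

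**What the plan says.** **What is promised.** The synopsis and Section 2.4.1 name three means of assessing safety against placebo: adverse events, vital signs and safety bloods. Section 2.4.2 turns the third into an endpoint: "Incidence of Safety Blood Parameter AEs by product allocation".

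**What is scheduled.** In Table 2 (Section 6), the row "Safety blood parameters", continued over the page as "Chemistry profile and Hematology profile", has one mark, under Visit 1. Visit 2, Visit 3 and Early Termination are empty. The row above it, "Vitals (Blood pressure, heart rate, temperature"), is marked at all four. Section 8.1 adds only: "A total of approximately 7.5mL/0.25 fl.oz of blood should be collected from all Participants". It gives no number of draws and no later time point.

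**What other sections assume.** Section 11.2.4 treats a laboratory change as an adverse event when it is a clinically significant worsening from baseline. It then gives a rule that begins "If, at the end of the treatment phase, there are abnormal clinical laboratory". Section 9 asks that withdrawn participants have a final assessment with the "standard medical and laboratory tests which would have been done on normal completion of the study". Section 11.5 requires clinically significant laboratory values to be judged for their relationship to the product.

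**The concern.** The objectives, the endpoint list and the safety rules describe a trial that measures blood on product. The schedule that the site will follow describes a trial that measures blood once, to decide eligibility. Both cannot hold.

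If Table 2 is followed, the final report will still have to fill a line for laboratory adverse events by arm, and the entry will be close to zero in both. A reader who does not check the schedule may well take this as evidence that the product does not disturb blood chemistry or hematology. An analysis plan cannot repair this, because no analysis can supply values that were never collected. The loss becomes permanent as each participant passes Visit 3.

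**Working it through.** **1. The plan's own numbers.** Section 4.1 gives 80 randomized (40 per arm), 10% dropout and 72 evaluable. 80 × (1 − 0.10) = 72, and 72 / 0.90 = 80, so these agree. With equal arms, 72 / 2 = 36 evaluable per arm.

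**2. Timing of the only draw.**

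| Event | Day | Source |
|---|---|---|
| Safety bloods | -21 to -15 | Table 2, Visit 1 |
| Randomization | 0 | Table 2, Visit 2 |
| First dose | 1 | Section 5.5.1: "Participants will consume their first dose of Study Product on the day following their Visit 2 (Day 1") |
| End of intervention | 56 (+3) | Table 2, Visit 3 |

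The draw falls 16 to 22 days before the first dose (1 − (−15) = 16; 1 − (−21) = 22). Scheduled draws before dosing: 1. Scheduled draws after dosing: 0.

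**3. Can that draw produce the endpoint?** Section 11.2.4 needs a baseline and a later value. Visit 1 supplies the baseline, and nothing scheduled supplies the later value. The draw cannot produce an event by itself either. Exclusion criterion 15 keeps out anyone with a clinically significant abnormal screening result, and the adverse event row in Table 2 has no mark under Visit 1 or the run-in.

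**4. Number of on-product safety blood results planned.** 0 of 40 per arm, 0 of 80 in total.

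**5. What the endpoint could say with and without measurement.** If n participants are tested and none has an event, the exact one-sided 95% upper limit for the event rate is 1 − 0.05^(1/n).

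- n = 40 per arm (all randomized): 1 − 0.05^(1/40) = 7.2%.
- n = 36 per arm (evaluable): 1 − 0.05^(1/36) = 8.0%.
- n = 0 (as scheduled): no limit; any rate is compatible with the data.

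**6. What one repeat panel would detect.** The chance of at least one event in an arm is 1 − (1 − p)^n. The true rates p below are illustrative assumptions, since the protocol gives none.

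| p | n = 36 | n = 40 |
|---|---|---|
| 1% | 30% | 33% |
| 2% | 52% | 55% |
| 5% | 84% | 87% |
| 10% | 98% | 98.5% |

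A single repeat panel would be a modest safety screen, but it would put data behind the endpoint.

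**The case against.** - **The table may have lost a mark.** The safety blood row is split by a page break, so a missing mark is somewhat likelier here than elsewhere. Both halves can be read, however. The only mark is under Visit 1, neighboring rows are intact, and no other section schedules a later draw. This is a caveat and does not rebut the point.
- **The blood volume proves little.** This is right. Section 8.1 gives a total without tube sizes or number of draws. It is compatible with a single draw but does not establish one, and the conclusion does not depend on it.
- **Section 9 need not mean bloods.** Table 2 does schedule a urine pregnancy test at Visit 3 and Early Termination, which could be the laboratory test meant. So Section 9 is weaker support, and the count of zero is a count of safety blood results, not of every laboratory test. Section 11.2.4 is the firmer support, although its wording is general and conditional.
- **The endpoint counts adverse events, which can arise without a scheduled test.** An unscheduled or outside test could reveal an abnormality, and Sections 11.1 and 11.5 would capture it. This stands as a limit on the claim: no scheduled assessment captures the endpoint. Ascertainment that depends on who happens to be tested elsewhere does not support a comparison of incidence between arms.
- **The primary endpoint is untouched.** True. Efficacy, randomization and sample size are unaffected, and general adverse events and vital signs are still collected. The defect is confined to one of the three listed safety assessments, for which the trial would still report a result.

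**Conclusion.** The point holds and should be corrected before the trial proceeds. As scheduled, the trial collects no on-product safety blood results in either arm (0 of 80 participants), so a stated safety objective cannot be answered and its endpoint would be reported with no systematic measurement behind it. A zero count would place no bound on the laboratory event rate, against 7.2% to 8.0% had 40 or 36 per arm been tested without an event.

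This rests on reading Table 2 as having a single mark in the safety blood row, and on no other study document adding a later draw. The upper limits are for comparison only; they assume one post-dose panel in everyone counted and no events.

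**What to change.** Reconcile Table 2 with the synopsis and Sections 2.4.1, 2.4.2, 8.1, 9, 11.2.4 and 11.5 before the first participant is randomized. There are two coherent ways to do it.

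1. **Drop the laboratory claim (least effort).** Remove safety bloods from the safety objectives in the synopsis and Section 2.4.1, and delete the laboratory endpoint from Section 2.4.2. Take out the wording in Sections 9 and 11.2.4 that presupposes end-of-treatment blood values. Keep the general rule for judging an abnormal result that turns up unscheduled. State that the Visit 1 panel serves only exclusion criterion 15. The report then makes no statement on laboratory safety.
2. **Keep the laboratory claim.** Mark the same panel at Visit 3 and Early Termination in Table 2, and revise the total blood volume in Section 8.1.

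**Cost.** The first option changes wording only, but it is still an amendment. Section 12.5 requires ethics approval, and Section 14.1 requires written agreement of sponsor and investigator before it takes effect. The second needs the same approvals plus one repeat panel per participant at a visit that already exists. Once a participant has passed Visit 3 the second option is closed for that person, so the decision should not wait for the analysis plan.
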